3.3.2 Inclusion criteria

1. WOCBP¹ must be ready and able to use highly effective methods of birth control per ICH M3 (R2) that result in a low failure rate of less than 1% per year when used consistently and correctly from date of screening until 4 weeks after last treatment in this trial. A list of contraception methods meeting these criteria is provided in the patient information.

(¹ A woman is considered of childbearing potential (WOCBP), i.e. fertile, following menarche and until becoming post-menopausal unless permanently sterile.

Permanent sterilisation methods include hysterectomy, bilateral salpingectomy and bilateral oophorectomy. Tubal ligation is NOT a method of permanent sterilisation.

A postmenopausal state is defined as no menses for 12 months without an alternative medical cause.)

- 2. Patients with moderate-to-severe plaque PsO who have completed treatment in the preceding trial without early discontinuation, agree to continue treatment in 1407-0005, and
- for patients entering from Part 1 of trial 1407-0030

Page 30 of 84

- o achieve a ≥PASI50 response upon completing the trial 1407-0030 Week 24 end-of-treatment visit
- for patients entering from Part 2 of trial 1407-0030
 - o achieve a ≥PASI50 response upon completing the trial 1407-0030 Week 12 endof-treatment visit or perceived patient improvement, at the discretion of the Investigator
- 3. Signed and dated written informed consent in accordance with ICH-GCP and local legislation prior to admission to the trial.

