4.1.3 Method of assigning patients to treatment groups

For patients entering from Part 1 of trial 1407-0030, during visit 1, eligible patients will continue to receive their treatment allocation of BI 730357 received in the preceding study, in a blinded fashion, via Interactive Response Technology (IRT). Upon completion of Visit 2/Week 12 the patients in this extension study will be assigned to an open label BI 730357 dose, via IRT (refer to Section 3.1).

Patients entering from Part 2 of trial 1407-0030 will all be assigned to open label BI 730357 400 mg q.d.

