6.2.2 Treatment period

The treatment period starts with Visit 1 and ends with the EOT visit. The patients will be fasted for each visit.

The patients will return to the clinic for regularly scheduled visits as specified in the Flow Chart. At these visits, the occurrence of safety and efficacy endpoints, trial medication compliance, concomitant therapy or intervention will be assessed.

At all treatment visits, the order of assessments (as applicable) should be followed:

- Completion of the questionnaires
- Physical examination, urine pregnancy, vital signs, and ECG
- Laboratory samples

All assessments must be performed before the medication is taken.

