Patients from part 1 of trial 1407_00030 who discontinue study treatment prior to Week 12 will be excluded from the second and fourth sets of analyses above. Due to varying length of exposure to the various doses, exposure adjusted incidence rates will be presented in addition to number and percentage of patients with events in the fifth set above (classification by dose at onset).

For the analysis of other safety data (laboratory data, vital signs ,suicidal ideation) summaries will be presented for the entire study, for the first 12 weeks of the study and after 12 weeks on study. For these outputs data from patients who rolled over from Part 1 and Part 2 of study 1407-0030 will be combined. In some of these data displays each treatment appears on a separate page. If deemed appropriate, additional displays showing descriptive statistics with figures for selected outcomes will be presented.

For efficacy summaries of response at Week 24 all patients from Part 1 of trial 1407-0030 will have data will be grouped as follows:

- 100 mg patients from part 1 of trial 1407-0030
 - 25 mg/100mg
 - 50 mg/100 mg
 - 100 mg/100mg
- 200 mg patients from part 1 of trial 1407-0030
- All patients from part 1 of trial 1407-0030
- 400 mg patients from part 2 of trial 1407-0030
- All patients from part 1 and part 2 of trial 1407-0030 combined

For efficacy summaries of time to loss of response data will be grouped as follows:

- 100 mg patients from part 1 of trial 1407-0030 (combing 25 mg/100mg, 50 mg/100 mg and 100 mg/100mg)
- 200 mg patients from part 1 of trial 1407-0030
- 400 mg patients from part 2 of trial 1407-0030

Efficacy response at Week 12 and 36 for patients from Part 2 of trial 1407-0030 will be summarized.

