6.7 BASELINE, TIME WINDOWS AND CALCULATED VISITS

For all analyses, baseline refers to the baseline value in the 1407-0030 study.

For laboratory safety measurements, the last measurements taken prior to the intake of BI 730357 or placebo will be considered as baseline.

In general, measurements reported with a date only (and no time) and taken on the day of first administration of trial treatment will also be considered pre-treatment values.

The visit schedule with accompanying details can be found in Flow Chart in the CTP. Measurements taken after start of treatment will be considered either on- or off-treatment values based on definition in [Table 6.1: 1](#).

On-treatment measurements for EOT and EOS visit for early discontinued patients will be allocated to visits by means of time windows with the limit between adjacent windows half-way between the planned dates for the visits; the middle day is counted to the window of the later visit. Mutually exclusive relative day windows are defined below to provide derived visits that correspond to the post-baseline time points. For example, Visit 2 is planned on Day 84 and Visit 3 is planned on Day 168. Therefore, the window of Visit 2 reaches until Day 125 while the window of Visit 3 starts on Day 126. The visit schedule with corresponding windows is given in the following table.

Table 6.7: 1 Time windows for patient visits

Window No.	Window label	Nominal visit	Nominal day	Interval
1	Day 1	Visit 1	1	N/A
2	Week 12	Visit 2	84	[2, 125]
3	Week 24	Visit 3	168	[126, 209]
4	Week 36	Visit 4	252	[210, 293]
5	Week 48	Visit 5	336	[294, 377]
6	Week 60	Visit 6	420	[378, 461]
7	Week 72	Visit 7	504	[462, 545]
8	Week 84	Visit 8	588	[546, 629]
9	Week 96	Visit 9	672	[630, 713]
10	Week 108	Visit 10	756	[714, 797]
11	Week 120	Visit 11	840	[798, 881]
12	Week 132	Visit 12	924	[882, 965]
13	Week 144	Visit 13	1008	[966, 1049]
14	Week 156	Visit 14	1092	[1050, 1133]
15	Week 168	Visit 15	1176	[1134, 1217]
16	Week 180	Visit 16	1260	[1218, 1301]
17	Week 192	Visit 17	1344	[1302, 1385]
18	Week 204	Visit 18	1428	[1386, 1469]
19	Week 216	Visit 19	1512	[1470, 1553]
20	Week 228	Visit 20	1596	[1554, 1637]
21	Week 240	Visit 21	1680	[1638, 1721]
23	Week 252	Visit 22	1764	[1722, 1805]
24	Week 264	Visit 23	1848	[1806, 1889]
25	Week 276	Visit 24	1932	[1890, 1973]
26	Week 288	EOT	2016	[1974, 2029]
27	Week 292	EOS	2044	[2030, ∞]

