7.5 SECONDARY ENDPOINT(S)

7.5.1 Key secondary endpoint(s)

This section is not applicable as no key secondary endpoint has been specified in the protocol.

7.5.2 (Other) Secondary endpoint(s)

For the convenience of writing and reviewing, all PASI and sPGA endpoints at different time points (secondary and further clinical endpoints) are first described generally in this section prior to addressing each secondary objective specifically.

Psoriasis Area and Severity Index (PASI)

Details for scoring Psoriasis Area and Severity Index (PASI) and its components are described in Section 10.1 of the CTP. The percent reduction from baseline is calculated by % PASI reduction from baseline = $((\text{PASI at baseline} - \text{PASI at Visit X}) / \text{PASI at baseline}) * 100$, at all visits with PASI collected. Achieving an X% or larger reduction from baseline PASI score is denoted as PASI X.

Static Physician's Global Assessment (sPGA)

The sPGA is scored using the following levels of assessment:

0 - clear 1 - almost clear 2 - mild 3 - moderate 4 - severe

Secondary Outcome Achievement of PASI50/PASI75/PASI90/PASI100 at Week 24

Descriptive statistics of the percentage of patients who achieve a PASI score of at least 50% (PASI 50), 75% (PASI 75), 90% (PASI90) and 100% (PASI100) reductions from baseline at Week 24 will be tabulated for each treatment group. The number of patients, number of patients attaining the PASI response, percentage of patients attaining the PASI response at Week 24 with corresponding exact 95% confidence interval will be presented based on the Clopper Pearson method.

The primary analysis of these secondary outcomes will be based on an observed case analysis.

Secondary Outcome Achievement of sPGA clear or almost clear at Week 24

Descriptive statistics of the percentage of patients who achieve sPGA of clear or almost clear (sPGA score of 0 or 1 ("clear or almost clear")) at Week 24 will be tabulated for each treatment group. The number of patients, number of patients attaining the sPGA response, percentage of patients attaining the sPGA response at Week 24 with corresponding exact 95% confidence interval will be presented based on the Clopper Pearson method.

The primary analysis of these secondary outcomes will be based on an observed case analysis.

Secondary Outcome Achievement of sPGA clear at Week 24

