Descriptive statistics of the percentage of patients who achieve sPGA of clear (sPGA score of 0 ("clear ")) at Week 24 will be tabulated for each treatment group. The number of patients, number of patients attaining the sPGA response, percentage of patients attaining the sPGA response at Week 24 with corresponding exact 95% confidence interval will be presented based on the Clopper Pearson method.

The primary analysis of these secondary outcomes will be based on an observed case analysis.

Secondary Outcome Time to Loss of PASI50/PASI75/PASI90/PASI100 for patients who achieve the response up to Week 288

For the time to loss of response (PASI 50/ PASI 75/ PASI 90/ PASI 100) the time to event will be calculated as

- Time to first loss (with observed event) = [date of first loss] – [date of first visit with qualifying response] + 1
- Time to first loss (censored) = [date of last visit with qualifying response] – [date of first visit with qualifying response] + 1
- If a patient never attains PASI 50/ PASI 75/PASI 90/PASI 100 then the patient will not contribute to the analysis of this outcome.

Time to loss of response will be analysed descriptively by Kaplan Meier curves. If at least 50% of patients lose response, the median time to loss of response will be estimated median of time to loss with 95% confidence interval will be presented.

Secondary Outcome Time to Loss of sPGA clear or almost clear at Week 24 for patients who achieve the response up to Week 288

For the time to loss of response (sPGA clear or almost clear), the time to event will be calculated as:

- Time to first loss (with observed event) = [date of first loss] – [date of first visit with qualifying response] + 1
- Time to first loss (censored) = [date of last visit with qualifying response] – [date of first visit with qualifying response] + 1
- If a patient never attains sPGA clear or almost clear then the patient will not contribute to the analysis of this outcome.

[figure not shown]
Time to loss of response will be analysed descriptively by Kaplan Meier curves. If at least 50% of patients lose response, the median time to loss of response will be estimated median of time to loss with 95% confidence interval will be presented.

Secondary Outcome Time to Loss of sPGA clear at Week 24 for patients who achieve the response up to Week 288

For the time to loss of response (sPGA clear), the time to event will be calculated as:

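### The pooled 100 mg time-to-loss curve counts Week 12 losses on 25 or 50 mg that precede any 100 mg dose; the three dose sequences should be shown separately

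*SAP*

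**What the plan says.** SAP 6.1 (Treatment(s)) sets three groups for time to loss of response: 100 mg, 200 mg and 400 mg. The first is defined as "100 mg patients from part 1 of trial 1407-0030 (combing 25 mg/100mg, 50 mg/100 mg and 100 mg/100mg". For response at Week 24 the same section lists the three sequences separately under the 100 mg heading.

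SAP 7.5.2 defines the event time as "Time to first loss (with observed event) = [date of first loss] – [date of first visit with qualifying response] + 1". PASI reduction is derived "at all visits with PASI collected", and SAP 6.7 adds: "For all analyses, baseline refers to the baseline value in the 1407-0030 study".

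Under Protocol 3.3.2, Part 1 patients must "achieve a ≥PASI50 response upon completing the trial 1407-0030 Week 24 end-of-treatment visit". The Flow Chart footnotes place Visit 1 on the day of that end-of-treatment visit. Protocol 3.1 keeps Part 1 patients on their blinded dose until Visit 2/Week 12. Protocol 4.1.3 then says: "Upon completion of Visit 2/Week 12 the patients in this extension study will be assigned to an open label BI 730357 dose". Protocol 6.2.2 fixes the order within a visit: "All assessments must be performed before the medication is taken".

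SAP 6.1 also states as a general rule that patients are analysed by the treatment they actually received.

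**The concern.** The curve is labelled by the open-label dose, but its clock can start 12 weeks before 25 mg and 50 mg patients take that dose. Because the endpoint is first loss, a patient who loses response on 25 mg and regains it on 100 mg stays an event and adds no time in response on 100 mg.

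Elsewhere the SAP handles the switch with care. It splits Part 1 adverse events at the first intake after re-assignment, classifies them in a further analysis by dose at onset, and divides exposure by actual dose. Time to loss has no landmark, delayed start or split by sequence.

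Long-term efficacy is part of the main objective, and time to loss is the only visible secondary endpoint that runs past Week 24. Curves labelled 100, 200 and 400 mg will be read as durability on those doses.

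**Working it through.** The plan gives no figure for this endpoint to reproduce, so the check sets the definitions against the schedule and then illustrates the size.

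**Attribution**
1. Clock start: first visit with a qualifying response, at any visit with PASI collected, judged against the 1407-0030 baseline (SAP 7.5.2, 6.7). A response can therefore already exist at Visit 1.
2. Status at Visit 1: all Part 1 entrants have at least a PASI50 response (Protocol 3.3.2). Some may also meet PASI75/90/100 or the sPGA criteria.
3. Next PASI/sPGA for Part 1: Visit 2, nominal Day 84 (Flow Chart; SAP Table 6.7: 1). Visits 1.1 to 1.3 do not apply to Part 1.
4. First 100 mg dose for 25 mg and 50 mg patients: after the Visit 2 assessments.

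For a Visit 1 responder found to have lost response at Visit 2, event time = 84 − 1 + 1 = 84 days. Days on 100 mg by then, if the blinded dose was 25 or 50 mg: 0.

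**Mix of doses**
The protocol synopsis allows 0–40 patients on 25 mg, 0–80 on 50 mg and 0–80 on 100 mg in the blinded period, and 80–140 on open-label 100 mg. Lower-dose entrants could be none of the pooled group (0 + 0 + 80) or all of it (40 + 80 + 0 = 120).

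**Size, with assumed loss rates**
First step of the pooled curve: S = 1 − Σ(nᵢqᵢ)/Σnᵢ, where nᵢ is the number responding at Visit 1 and qᵢ the proportion lost at Week 12.

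- *Unequal rates.* n = 20/40/40 on 25/50/100 mg; q = 30%/20%/10%. Losses = 6 + 8 + 4 = 18. Pooled S = 1 − 18/100 = 0.82, against 0.90 for 100/100 mg. Share of losses on 25 or 50 mg = 14/18 = 78%.
- *Equal rates.* Same n; q = 10% throughout. Losses = 2 + 4 + 4 = 10. Pooled S = 0.90, unchanged, but 6 of the 10 losses are still on 25 or 50 mg.
- *Range.* For five mixes (25 mg 0–40, 50 mg 30–80, 100 mg 20–80) and assumed losses of 10–40%, 10–30% and 10%, the share of Week 12 losses on 25 or 50 mg runs from 33% to 95%, and pooled S from 0.90 down to 0.70.
- *Carried to Week 48.* Assume 10% loss per later 12-week interval in every sequence. In the unequal-rate example the pooled curve gives 0.82 × 0.9³ = 0.60, against 0.9⁴ = 0.66 for 100/100 mg. In a mild case, with a quarter of the group on lower doses and 20% loss there, Week 12 loss is 0.25 × 0.20 + 0.75 × 0.10 = 0.125, and Week 48 retention is 0.875 × 0.9³ = 0.64.

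These figures apply directly to PASI50, where all entrants start at Visit 1. For the other criteria, patients who first respond at Week 12 or later start at or after the switch and dilute the effect.

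**The case against.** **The start visit is not stated outright.** SAP 5.2.2 derives PASI reduction at follow-up visits, SAP Table 6.7: 1 gives Day 1 no window, and the Flow Chart footnotes treat the Visit 1 PASI as part of the preceding trial's last visit. If Visit 1 did not count, the earliest start would be Week 12 and the problem would largely disappear. This doubt stands. The analysis section itself (SAP 7.5.2) uses the broader wording, and counting 1407-0030 visits would start the clock earlier still.

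**Direction.** A reader might infer that the 100 mg curve is biased downwards and the contrast with 200 and 400 mg distorted against it. The documents do not support that. They give no loss rates, and every Part 1 entrant was selected as a responder on the current dose. Patients on 100 mg may also move up to 200 mg. SAP 7 makes 200 mg their planned dose from then on, but no section says which time-to-loss group holds them, so the net direction is unknown.

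**No formal comparison.** The trial tests no hypothesis, and the pooling is disclosed in the group definition. The 400 mg group also differs in fed dosing, entry rule and permitted delay before Visit 1. All true. The harm is to the reading of a descriptive curve and its median, not to an error rate.

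**Restarting the clock at Week 12.** This may look like the natural repair. It would condition the Part 1 curves on response at or after Week 12, drop genuine early losses on 100/100 and 200/200 mg, and admit patients who lost and regained response, while the 400 mg curve still ran from Day 1. It cannot replace the main analysis.

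**Conclusion.** The attribution fault holds, given that Visit 1 counts as a qualifying visit. For 25/100 and 50/100 mg patients already in response at Visit 1, a loss first seen at Week 12 precedes any 100 mg dose, yet it is an event in the 100 mg curve. This conflicts with the SAP's own as-treated rule. It can affect every such patient for PASI50, and for the other criteria only those who already met them at Visit 1.

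It would go too far to say that every Week 12 loss on a lower dose is affected. A patient who stops at or before Week 12 never receives 100 mg, and the SAP does not say which time-to-loss group that patient joins.

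If loss is faster on 25 or 50 mg, the pooled curve understates durability on 100 mg. If loss rates are equal, the curve does not shift. The size therefore rests on assumed rates. In the illustrations, pooled Week 12 retention is 0.70 to 0.90 against 0.90 for 100/100 mg. The SAP should be changed, but nothing in the trial's conduct depends on it.

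**What to change.** In SAP 6.1 and 7.5.2:

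- Present time to loss separately for 25/100, 50/100 and 100/100 mg, using the layout that SAP 6.1 already has for Week 24 response.
- Tabulate losses between Visit 1 and Visit 2 by the blinded dose actually taken.
- If a pooled curve is kept, label it as including time before 100 mg.
- State that Visit 1 counts as a qualifying visit, and align SAP 5.2.2 with 7.5.2.
- State which group holds patients who move from 100 to 200 mg.
- A Week 12 start among patients then in response may be added as a supportive analysis only, with its selection described.

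This needs SAP wording and programming but no new data. The price is smaller groups and wider intervals for each sequence. Some medians may go unreported, since the SAP gives a median only when at least half of the patients lose response.

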It is expected that Visit 1 of trial 1407-0005 will be performed on the same day of the EOT Visit of trial 1407-0030 in both patient groups. In the event that patients completing Part 2 of trial 1407-0030 are not able to be entered immediately into the extension trial due to administrative reasons (e.g., pending protocol approval, availability of trial medication), Visit 1 of the extension trial may be delayed for no more than 16 weeks.

The treatment period in this trial will be approximately 6 years.

Figure 6.1: 1

Trial 1407-0005 dose assignment/reassignment for patients entering from Part 1 of trial 1407-0030

[figure not shown]
[figure not shown]

Figure 6.1: 2

Trial 1407-0005 dose assignment for patients entering from Part 2 and continuing from Part 1 of trial 1407-0030

Dose selection at Week 12 is based on the safety and tolerability data from the SRD Trial 1407.1 and the MRD Trial 1407-0002, and will be contingent on DMC evaluation of all available data from Phase II trial 1407-0030. For patients entering from Part 1 of trial 1407-0030, if an unacceptable risk regarding the safety of the 200 mg dose level is reported by the DMC, the open label BI 730357 dose assignments beginning at Week 12, is to be altered to assign all patients to the 100 mg *q.d.* dose group.

All patients entering from Part 2 of trial 1407-0030 are to receive the 400 mg *q.d.* dose, as long as no unacceptable risks are identified during Part 2 of trial 1407-0030. Once Part 2 patients begin enrolling in this trial, existing patients receiving 100 mg *q.d.* in this trial will be given the option to titrate up to the 200 g *q.d.* dose, if the investigator determines that the Patients may benefit from the higher dose.

The first Part 2 patients enrolled in this study on December 10, 2020 and at that time all Part 1 patients had been in the study more than 12 weeks and had titrated to 100 mg *q.d.*

Subjects will be analyzed according to the treatment to which they were treated. The following study periods based on actual start and stop dates of study treatment administration are defined as follow.

Table 6.1: 1 Definition of Treatment Periods

Analysing Treatment Period	Start Date	Stop Date
Screening [#]	NA	NA
On-treatment*	Date/Time of the first administration of trial treatment	Date of the last administration of trial treatment + REP
Follow-up	Date of the last administration of trial treatment + REP+1 day	Date of the last per protocol visit

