6.6.1 Efficacy data

An observed case analysis will be performed for the primary analysis of the secondary outcomes PASI 50, PASI 75, PASI 90, PASI100, and sPGA clear or almost clear endpoints at week 24.

For the secondary outcome time to loss of PASI50/PASI75/PASI90/PASI100 for patients who achieve the response up to Week 288, patients who do not have the PASI assessment performed at a visit and maintained the PASI response at all scheduled visits prior to the missing visit will be treated as censored at the day after the last visit where the PASI response was attained.

For the secondary outcome time to loss of sPGA clear or almost clear for patients who achieve the response up to Week 288, patients who do not have the sPGA assessment performed at a visit and maintained the sPGA response at all scheduled visits prior to the missing visit will be treated as censored at the day after the last visit where the sPGA response was attained.

For the secondary outcome time to loss of sPGA clear for patients who achieve the response up to Week 288, patients who do not have the sPGA assessment performed at a visit and maintained the sPGA response at all scheduled visits prior to the missing visit will be treated as censored at the day after the last visit where the sPGA response was attained.

[REDACTED]

[REDACTED]

[REDACTED]

If at any time a patient uses an inappropriate concomitant medication, then all future data will be excluded for binary variables and for continuous variables and will not be implemented beyond the date of the prohibited medication..

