7. PLANNED ANALYSIS

The format of the listings and tables will follow the standards defined in the BI corporate guideline “Reporting of clinical trials and project summaries” .

The individual values of all patients will be listed, sorted by treatment, patient number and visit. The listings will be included in Appendix 16.2 of the CTR.

For EoT tables, the set of summary statistics is: N / Mean / SD / Min / Median / Max.

For appendix tables, the set of summary statistics is: N / Mean / SD / Min / Q1 (lower quartile) / Median / Q3 (upper quartile) / Max.

Tabulations of frequencies for categorical data will include all possible categories and will display the number of observations in a category as well as the percentage (%) relative to the respective treatment group. Percentages will be rounded to one decimal place. The category “missing” will be displayed only if there are actually missing values. Percentages will be based on all patients in the respective patient set no matter whether they have non-missing values or not.

No interim analysis is planned for this trial.

For patients from Part 1 of the 1407-0030 trial planned treatment for first 12 weeks of treatment is defined as treatment patient received at the end of 1407-0030. Planned treatment for after 12 weeks (Period 2) is defined as the treatment patient assigned from IVRS at week 12 visit (V2). For patients who titrate according to the protocol from 100 g *q.d.* dose to 200 g *q.d.* dose, if the investigator determines that the patient may benefit from the higher dose, 200 g *q.d.* dose will be the planned dose after the titration.

Subject data listings of data used in the analyses (i.e. demographic and baseline characteristics and key efficacy endpoints) will also be provided and included in Appendix 16.2 of the CTR.

Disposition of the patient population participating in the trial will be summarised by presentation of the frequency of patients screened, entered, screened but not entered, treated, entered but not treated. Within treated patients, data for patients rolled over from Part 1 of trial 1407-00030 will be summarized by treatment periods (period 1 - first 12 weeks of treatment and period 2 – open label treatment after week 12) for treatment ongoing patients, patients complete planned treatment period and patients who are prematurely discontinued, by reason.

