- Time to first loss (with observed event) = [date of first loss] – [date of first visit with qualifying response] + 1
- Time to first loss (censored) = [date of last visit with qualifying response] – [date of first visit with qualifying response] + 1
- If a patient never attains sPGA clear then the patient will not contribute to the analysis of this outcome.

Time to loss of response will be analysed descriptively by Kaplan Meier curves. If at least 50% of patients lose response the median time to loss of response will be estimated median of time to loss with 95% confidence interval will be presented.

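### The 100 mg time-to-loss-of-response curve can include response kept, or first reached, on 200 mg

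*SAP*

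**What the plan says.** Protocol 3.1 and 4.1.2, and SAP 6.1, give Part 1 patients on open-label 100 mg the option of 200 mg once Part 2 patients are enrolling, if the investigator thinks they may benefit. SAP 6.1 dates this: "The first Part 2 patients enrolled in this study on December 10, 2020", when every Part 1 patient was already past Week 12. SAP 7 adds that for a patient who goes up, the 200 mg "dose will be the planned dose after the titration".

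For time to loss of response, SAP 6.1 names three groups: 200 mg from Part 1, 400 mg from Part 2, and "100 mg patients from part 1 of trial 1407-0030 (combing 25 mg/100mg, 50 mg/100 mg and 100 mg/100mg". There is no 100 mg to 200 mg group. The general rule earlier in the same section is "Subjects will be analyzed according to the treatment to which they were treated".

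The endpoint is headed "Secondary Outcome Time to Loss of PASI50/PASI75/PASI90/PASI100 for patients who achieve the response up to Week 288" in SAP 7.5.2. Time is counted from the "date of first visit with qualifying response] + 1" to the first loss, or to the last visit with response if no loss is seen. In SAP 6.6.1 the time-to-loss censoring rule for PASI concerns "patients who do not have the PASI assessment performed at a visit and maintained the PASI response at all scheduled visits" before the missed one, and sPGA is handled the same way. The only visible rule there about a change of treatment is for prohibited medication: "If at any time a patient uses an inappropriate concomitant medication, then all future data will be excluded for binary variables", and likewise for continuous variables.

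**The concern.** The increase to 200 mg is a planned feature of the trial, and the option was already open when the SAP was finalised on 3 March 2021. Yet nothing visible in the grouping, clock or censoring rules acts on it. The natural reading is that a patient who goes up stays in the 100 mg group and keeps contributing response time.

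Dose mixing enters in two ways. A patient already in response may keep it on 200 mg. A patient may also first reach a response on 200 mg and then start a clock in the 100 mg curve, because the clock can start at any visit up to Week 288. The second route is nearly closed for PASI50, since Part 1 entry required it (Protocol 3.3.2). It is open for PASI75, PASI90, PASI100 and the sPGA responses. A patient who lost a given response before going up is unaffected for that response.

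Time to loss is a secondary endpoint shown by dose. Readers will take the curve and its median as durability on 100 mg. The rationale recorded for Global Amendment 3 (Protocol 11.3) calls 100 mg sub-optimal, so overstated 100 mg durability is the direction the sponsor would itself expect.

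**Working it through.** The plan gives no event rate, response-loss rate or uptake for this endpoint, so it has no figure to reproduce. The check covers how the rules apply, how much follow-up is exposed, and an illustration of size.

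**1. Following one patient through the rules.** Take a 50/100 mg patient in PASI75 response who moves to 200 mg.
- SAP 6.1 grouping: the sequence 50/100 mg places the patient in the 100 mg group.
- SAP 6.3: the Treated Set used for all efficacy analyses is keyed to treatment at the enrolment visit, so it does not move the patient.
- SAP 7: the planned dose becomes 200 mg, but this is not linked to the time-to-loss groups. If it were used to move the patient, response time earned on 100 mg would be credited to 200 mg, so the mixing would only change curves.
- SAP 6.6.1 and 7.5.2: no visit is missed and no prohibited drug is taken, so nothing stops the clock.

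**2. Follow-up after the option opened.**
- The first protocol date is 5 December 2018 (Protocol synopsis). To 10 December 2020 is 365 + 366 + 5 = 736 days, and 736 / 7 = 105.1 weeks. On that date no Part 1 patient could be past about Week 105, and all were past Week 12.
- Scheduled PASI/sPGA visits after Week 12 are Weeks 24 to 288 every 12 weeks: (288 − 24)/12 + 1 = 23.
- For the earliest possible entrant, the visits still to come are Weeks 108 to 288: (288 − 108)/12 + 1 = 16. The Week 108 window opens on day 756 − 7 = 749, after day 736.
- So 16 to 23 of 23 visits (16/23 = 70%, up to 100%) fall after the option opened. This shows when the option existed. It is not an effect size.

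**3. Illustration: response kept on 200 mg (all inputs assumed).** One-year retention on 100 mg is 60%, constant hazard; a share f of those still responding goes up at one year; HR is the hazard ratio for loss afterwards.

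S(3) = (1 − f) × 0.60³ + f × 0.60 × 0.60^(2·HR)

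On 100 mg alone, 0.60³ = 0.2160. With f = 0.25 and HR = 0.50: 0.75 × 0.2160 + 0.25 × 0.60 × 0.60 = 0.1620 + 0.0900 = 0.2520.

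| HR | f = 5% | f = 25% |
|---|---|---|
| 0.50 | 22.3% | 25.2% |
| 0.75 | 21.9% | 23.2% |
| 1.00 | 21.6% | 21.6% |
| 1.25 | 21.4% | 20.4% |

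The error runs from 0 to +3.6 points for HR 0.50 to 1.00, and from −0.2 to −1.2 points at HR 1.25.

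**4. Illustration: response first reached on 200 mg (all inputs assumed).** Median retention on 100 mg is 72 weeks, so λ = ln 2 / 72, and a share g of the group's responders first responds on 200 mg:

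S(t) = (1 − g)·exp(−λt) + g·exp(−λ·HR·t)

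On 100 mg alone, S(96) = 39.7%. With g = 10% and HR = 0.7, S(96) = 41.0% and the median is 74.5 weeks. With g = 30% and HR = 0.5, S(96) = 46.7% and the median is 87.1 weeks.

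**The case against.** The strongest reply is that an investigator-led, protocol-permitted increase belongs to the Part 1 regimen. A curve that keeps these patients is then a legitimate treatment-policy summary, and keying efficacy to treatment at enrolment (SAP 6.3) fits that. This stands as a defence of the curve, and the curve should be kept. It does not defend a label that says 100 mg without mentioning 200 mg.

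The SAP also does not overlook the increase altogether: it repeats the option in 6.1 and updates the planned dose in 7. That is fair. What is missing is any link from those statements to this endpoint.

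Censoring at the increase may be informative, because the decision follows the investigator's view of benefit. This stands, and it is why both curves are needed.

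The illustrated error is modest beside sampling error. With 80 to 140 patients (the planned open-label 100 mg range), all assumed responders and none censored, the 95% half-width at 21.6% is 1.96·√(0.216 × 0.784/n), or 9.0 to 6.8 points. The 3.6-point case is about half of that or less. This limits the importance of the point, but sampling error shows in a confidence interval and mislabelled exposure does not.

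The trial tests no hypothesis (Protocol 7.2). The labelled curves and medians are then the result itself. Finally, parts of SAP 6.6.1 and other sections are redacted and a dosing figure is not shown, so a hidden rule cannot be excluded. The visible grouping, clock and missing-visit rules contain none.

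**Conclusion.** The concern holds on the visible text. Followed as written, the plan gives a secondary result labelled 100 mg that can mix in response on 200 mg, and this does not fit the SAP's own rule of analysis by treatment received. Adverse events get an additional analysis by dose at onset (SAP 6.1 and 7.8.1); no counterpart is visible for time to loss.

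The actual size is unknown and could be near zero. It depends on how many patients went up while in response, how many first responded afterwards, when, and how 200 mg compares with 100 mg; the documents give none of these. Under the assumptions in step 3, three-year retention is misread by between −1.2 and +3.6 points. The sign is positive if 200 mg holds response better and negative if patients who go up do worse. The issue affects how a descriptive secondary endpoint is read. It does not touch the primary safety endpoint or any test. It should be corrected, and the correction is cheap.

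**What to change.** In SAP 6.1 and 7.5.2:

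1. Relabel the existing curve as 100 mg with optional increase to 200 mg.
2. Add a 100 mg curve that counts only responses first reached before the first 200 mg dose. Censor it at the last visit with response on or before that dose. A loss recorded on or before that dose remains an event.
3. State that this censoring may be informative because the increase follows investigator judgement, and that both curves are shown for that reason.
4. Print, for each response definition, the number of patients who went up while still in response.

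The cost is a text change, one new label, one extra curve and one count before database lock. The only added input is the date of the first 200 mg dose, which the exposure summary by actual treatment (SAP 7.7) already requires. No protocol amendment is needed. A footnote that the after-Week-12 adverse event columns ending in 100 mg include time on 200 mg would be tidy but is optional, since the dose-at-onset set already assigns those events correctly.
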